8.3.2.6. Recording Methods in the e-CRF

Adverse events must be documented on the « Adverse Event » page of the e-CRF.

In case of chronic disease:

- if the disease is known when the participant enters in the study, only worsening (increased frequency and/or intensity of the episodes/attacks) will be documented as an adverse event,
- if the disease is detected during the study and if repeated episodes enable diagnosis of a chronic disease, the episodes will be grouped on the « Adverse Event » page previously created for the event which will clearly describe the diagnosis.

In case of gastrointestinal events (such as diarrhoea, loose stools, nausea, flatulence, vomiting, dyspepsia, abdominal pain, etc.):

- the investigator will specify, in the "description" area of the AE e-CRF form, the circumstances of occurrence, localisation, duration and frequency of the event.

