After repeated oral administration of S42909, steady-state is reached by Day 4, with no accumulation of the parent drug after 10 days of repeated administration of S42909 at 600, 1200 and 1800 mg (with standard meals). Food intake (High Fat High Calorie (HFHC) or standard breakfast) increases Cmax and exposure for S42909 and S45015. S45236 C_{max} and exposure are decreased at 600 mg after a HFHC breakfast.

Results of one combined study (PKH-42909-003) investigating the S42909 drug-drug interactions with a CYP2C9 substrate (warfarin) and with a CYP3A4 substrate (midazolam) showed that S42909 at the dose of 210 mg q.d does not interact with the elimination of warfarin or midazolam, in accordance with circulating concentrations much lower than K_i and supporting a low risk of drug-drug interaction with S42909.

Safety data in clinical studies

Overall, 278 subjects have been enrolled into the S42909 clinical studies; out of these, 203 have received at least one administration of S42909.

S42909 was administered in doses ranging from:

- 105 mg to 840 mg in oral single dose administration and 210 mg to 630 mg in oral repeated dose administration for periods between 5 and up to 14 days, in the Gelucire® 44/14 formulation (currently discontinued),
- 600 mg/day to 2100 mg/day in single oral dose administration and repeated dose administration with the newly developed formulation for 10 days.

Overall, S42909 was well tolerated up to the dose of 1800 mg in oral single dose and 1200 mg in oral repeated dose administration. There were no clinically relevant abnormalities concerning biologic and hematologic parameters, physical examination, vital signs or on ECG tracings.

The majority of the reported Treatment Related Emergent Adverse Events were mild or moderate, mainly diarrhoea probably due to the laxative effect of main excipient a cellulosic derivative.

During the conduct of the CL1-42909-013 dose-escalation study, diarrheic episodes were reported in several subjects starting from the daily dose of 1200 mg of S42909. The episodes increased in frequency, duration and severity when escalating the dose and at the same dose when passing from single dose administration to repeated dose administration. Typically, the episodes were mild to moderate in intensity occurring rapidly after study drug intake and resolved spontaneously the same day.

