8.3.1. Definitions

8.3.1.1. Adverse events

An adverse event is defined as any untoward medical occurrence in a subject participating in a clinical study, whether or not there is a causal relationship with the IMP and/or experimental procedures, occurring or detected from the date the participant signs the information and consent form, irrespective of the period of the study (periods without administration of the IMP (e.g. selection period) are also concerned).

An adverse event can therefore be:

- any unfavourable and unintended sign, including an abnormal finding from an additional examination (lab tests, X-rays, ECG, etc.) which is deemed clinically relevant by the investigator,
- any symptom or disease,
- any worsening during the study of a symptom or a disease already present when the participant entered the study (increase in frequency and/or intensity), including the studied pathology,

and detected during a study visit or at an additional examination or occurred since the previous study visit (including relevant event reported in participant's diary or safety evaluation scale).

Of note:

- Any **hospitalisation for social reasons, educational purpose** (e.g. learning of arterial hypertension management by the participant) or routine check-up, and the hospitalization for PK sampling purposes at W004 (participants having signed the consent form for the optional PK analysis) should not be considered as an adverse event and should not be reported in the e-CRF.
- The following procedures, whether planned before the study or not, whether leading to a hospitalisation or not, should be reported in the specific page "**Procedures not subsequent to an adverse event**" of the e-CRF:

- therapeutic procedures related to a non-aggravated medical history (e.g. cataract extraction not due to an aggravation of the cataract during the study, haemodialysis sessions related to a renal insufficiency not aggravated during the study),
- prophylactic procedures (e.g. sterilisation, wisdom teeth removal),
- comfort procedures (e.g. cosmetic surgery),
- control procedures of a pre-existing condition without aggravation (e.g. colonoscopy to control the remission of colon cancer).
- any hospitalisation to perform the duplex ultrasonography examination

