8.3.2.4. Follow-up of adverse events

The investigator must ensure that follow-up of the participant is appropriate to the nature of the event, and that it continues until resolution if deemed necessary.

Any change in terms of diagnosis, intensity, seriousness, measures taken, causality or outcome regarding an adverse event already reported must be written up in a new complete evaluation of the event documented on the “Adverse event” page previously created for the event in the e-CRF.

If the adverse event has not resolved at the participant's final visit in the study, the participant must be followed up suitably and any information on the outcome of the event will be noted on the « Adverse Event » page previously created for the event in the e-CRF.

If the follow-up of the participant is not done by the investigator him/herself (hospitalisation, followed by a specialist or the participant's general practitioner, etc.), the investigator will do everything to establish/maintain contact with the person/department in charge of follow-up of the participant.

8.3.2.5. Special situations (pregnancy, overdoses, intake of IMP by a person around the participant)

Pregnancy

If a female participant in the study becomes pregnant, the investigator must:

- stop immediately the IMP,
- report it on an « Adverse Event » page as well as on the specific paper pregnancy form to be notified immediately (ERIN),
- contribute to the follow-up of this pregnancy and provide the sponsor with information concerning this follow-up
- If the partner of a participant becomes pregnant during the course of the study or within 3 months after completion of study treatment, the pregnancy should not be reported in the e-CRF. The investigator should **immediately** contact the sponsor (contact details provided in the investigator's study file) who will inform him/her about the procedure to be followed.

Overdose of IMP

- In case of overdose, the investigator should report it on an “Adverse Event” page to be notified immediately (ERIN).
- Overdose should be followed-up to ensure that the information is as complete as possible with regards to:

- dose details (number of units, duration,...) and, if multiple overdose, details regarding other medicinal products or substance ,
- context of occurrence, i.e. intentional (suicide attempt, other reason) or accidental (error in prescription, administration, dispensing, dosage),

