3.6.1. Adverse events

Definition:

- Treatment Emergent Adverse Events (TEAE) are defined as all adverse events:
 - which occur between the first IMP intake date (included) and the last IMP intake date + 15 days (included)or
 - which occur before the first IMP intake date and which worsen (in terms of intensity) or become serious according to the investigator's opinion between the first IMP intake date (included) and the last IMP intake date + 15 days (included).

Note: + 15 days is calculated according to the half-life of the S42909.

Of note, in case of multiple information of the same event before the first IMP intake date, the information nearest to the first IMP intake date is taken into account.

The seriousness of the adverse event and the relationship with the IMP are based on the investigator's opinion but often also include the sponsor's decision to upgrade the seriousness and/or relation to the IMP (see TLG for details).

Analyses:

The number of events, the number and percentage of patients reporting at least one event, presented by primary system organ class (SOC) and/or preferred term (PT) (depending of the analysis) will be provided for :

- Serious AE over the study period according to the investigator's or sponsor's opinion.
- Treatment emergent AE (TEAE), TEAE leading to IMP withdrawal, TEAE requiring new treatment or increase of ongoing treatment, TEAE requiring surgical or medical procedure, TEAE related to IMP, serious TEAE, severe TEAE, non serious TEAE over the treatment period (EUDRACT), After treatment AE.

TEAE will be described according to the seriousness, the intensity, the relationship with the IMP, the action taken regarding the IMP, the requirement of added therapy and the outcome.

The medical concept of diarrhea, *i.e.* TEAE related to diarrhea, will be analysed through a listing. The MedDRA code list to use is the list n°3741 Diarrhoea medical concept M22.0.

A listing of deaths and ERIN will be provided.

A Listing of AE occurring after the treatment period will also provided.

The following information will be taken into account:

- For the analyses where the intensity of the adverse event is considered, the worst intensity from the day of emergence to the end of the studied period will be taken into account.
- For the analyses where the action taken regarding the IMP is considered, all the actions taken recorded from the day of emergence to the end of the studied period will be taken into account.

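### An adverse event opened in the placebo run-in that becomes more frequent, but not more intense, on treatment is not treatment-emergent under the SAP, although the protocol counts frequency as worsening

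*Protocol*

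**What the plan says.** **Protocol.**
- Section 8.3.1.1 includes in the AE definition the worsening of a symptom or disease present when the participant entered the study, and explains worsening as "increase in frequency and/or intensity".
- Section 8.3.2.6 uses the same meaning for chronic disease known at entry: "only worsening (increased frequency and/or intensity of the episodes/attacks) will be documented as an adverse event". For a disease detected during the study, "if repeated episodes enable diagnosis of a chronic disease, the episodes will be grouped" on the page already created. For gastrointestinal events, the investigator must enter frequency and duration in the description area of the AE form.
- Section 8.3.2.4 names the changes that call for a new evaluation on an existing AE page: "Any change in terms of diagnosis, intensity, seriousness, measures taken, causality or outcome regarding an adverse event already reported". Frequency is not among them.
- Section 8.3.2.1 and footnote 10 of Table (4.2.2) 1 put events before the first dose on the AE form if they are linked to study procedures or conditions. Other events before the first dose go to medical history.

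**SAP.** Section 3.6.1 gives two routes to a TEAE. The first is onset from the first IMP intake to 15 days after the last. The second covers events "which occur before the first IMP intake date and which worsen (in terms of intensity) or become serious" within that same window. Diarrhoea is shown in a listing restricted to TEAEs.

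**The concern.** The two documents use different meanings of worsening, and frequency appears in neither SAP route. An event already open at the first dose can therefore worsen in the protocol's sense without becoming treatment-emergent.

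The protocol gives a reason to care about frequency. On diarrhoea in the dose-escalation study, its background section reports: "The episodes increased in frequency, duration and severity when escalating the dose". The safety profile of each dose is a secondary objective. Whether a patient counts would also depend on how the investigator attributed a run-in symptom before randomisation, which has nothing to do with the drug.

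**Working it through.** There is no planned figure to reproduce. The check applies the two SAP routes to each way the protocol allows an event to be recorded.

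| Course of the event | Recording under the protocol | Status under SAP 3.6.1 |
|---|---|---|
| Chronic disease known at entry, more frequent after the first dose | New AE (8.3.2.6), onset on treatment | TEAE, first route |
| Run-in event filed as medical history, more frequent after the first dose | New AE (8.3.1.1, 8.3.2.1), onset on treatment | TEAE, first route |
| Run-in episode resolved, separate episode after the first dose | New AE page | TEAE, first route |
| AE page open at first dose, then more intense or serious | Re-evaluated on the same page (8.3.2.4) | TEAE, second route |
| AE page open at first dose, then more frequent, same intensity, not serious, no new page | Frequency at most in the description text | **Not a TEAE** |

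Only the last row is lost. The second and last rows can describe the same clinical course; they differ only in where the run-in event was first filed. The second row assumes that a run-in event filed as history is treated as pre-existing when its later worsening is recorded.

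**Where the lost case would appear.** Protocol 10.1.4 planned a table of all AEs, plus emergent and serious ones. SAP 3.6.1 tabulates serious AEs, TEAEs and their subsets, and after-treatment AEs. A non-serious event in the last row falls into none of these, nor into the diarrhoea listing. The separate tables and listings document is not available here, so a general AE listing there cannot be excluded.

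**Size per patient.** The SAP reports 121 included patients in six arms: 121 / 6 ≈ 20 per arm. One missed patient is 1 / 20 = 5 percentage points on that arm's row for the event's preferred term. This assumes equal arms, all patients in the Safety Set, and no other TEAE under the same term in that patient. Overall TEAE incidence does not move if the patient has any other TEAE.

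**The case against.** The case for leaving the text alone has several parts, and much of it stands.

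- **The 8.3.2.6 sentence does not itself show a loss.** A reader might infer that patients with known chronic disease are undercounted. They are not: their worsening after the first dose is a new AE and enters by the first route. The sentence shows only what the protocol means by worsening.
- **The grouping rule is narrow.** A reader might infer that repeated episodes are generally collected on the run-in page. The rule applies only when repeated episodes establish a chronic disease, which loose stools over 14 days need not do.
- **The protocol does not say that a frequency rise stays on the old page.** Its absence from the list in 8.3.2.4 could equally mean that it belongs on a new page. The loss is conditional on no new page being opened.
- **Filing of run-in placebo events is not settled.** Footnote 10 refers to products other than the IMP. The protocol's abbreviation list includes placebo under IMP, whereas the SAP reserves the term for treatment after randomisation. Recording on the AE form is plausible but not certain.
- **A concentrated undercount at the higher doses is not supported.** The background section says that severity and duration rose as well as frequency, and the intensity criterion catches the severity part. Episodes typically resolved the same day, so later ones would naturally be new AEs. Reports started at 1200 mg daily, which is only the top arm here, and the twice-daily schedule used in this trial reduced the frequency.
- **Other rules shrink the pool.** A history of chronic diarrhoea bars selection (criterion 38), and an AE that might compromise safety or any evaluation bars inclusion (criterion 72). Intensity is graded by interference with activity (8.3.2.2), so a troublesome rise in frequency may raise the grade anyway.

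What remains is the wording difference itself: nothing in the SAP's pre-dose rule lets a frequency rise count.

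**Conclusion.** The mismatch is real and narrow. It affects a non-serious AE page that is opened before the first IMP intake, is still open at that point, and afterwards records more frequent episodes at unchanged intensity, with no new page. Such an event is left out of the TEAE tables and the diarrhoea listing, although the protocol's own sense of worsening would include it.

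The number affected cannot be estimated, because the documents give no rate of AEs open at W000. A guessed percentage of patients with an open page would size only the pool at risk, not the number lost. The number is probably small. The conclusion assumes that run-in placebo events are filed on the AE form at least sometimes, and that a rise in frequency is sometimes left on the existing page. The point concerns descriptive safety reporting only; the primary analysis and sample size are untouched. Low severity; a cheap improvement.

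**What to change.** 1. In SAP 3.6.1, extend the second route so that a pre-dose event is treatment-emergent if it worsens in intensity or frequency, or becomes serious.
2. At the blind review already planned in protocol 14.2, flag AEs open at the first IMP intake whose description documents a rise in frequency after the first dose. Protocol 8.3.2.6 already requires that text for gastrointestinal events. The flag is needed because frequency is free text and cannot be programmed in the way an intensity grade can. Set it before unblinding.

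Two other changes are not recommended. Requiring that episodes after the first dose never share a page with earlier ones would turn unchanged continuing events into TEAEs. Amending the protocol's recording sections would come too late to alter most records, since the SAP reports that 121 patients were already included.

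Cost: one phrase in the SAP, a short blinded medical read of free text, and possibly a few more TEAEs.

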8.3.2.7. Procedure for an event requiring an immediate notification

In case of an event requiring an immediate notification, the investigator must:

- **Immediately** after being informed of this event, **fill in the participant's medical file** as well as the « **Adverse Event** » page of the e-CRF according to the general instructions available in the e-CRF, without waiting for the results of the clinical outcome or of additional investigations. When data will be submitted into Inform, an e-mail will be immediately and automatically sent to the sponsor.
- Provide the sponsor (person designated in the contact details provided in the investigator's study file), as they become available, with anonymized copies of the documents which provide additional useful information,
- Fulfil his/her regulatory obligations to the Competent Authorities and/or to the IRB/IEC, in accordance with local regulations.

If an adverse event initially judged as non-serious worsens and becomes serious (ERIN), this must be reported **immediately** on an "Adverse event" page of the e-CRF.

In case the e-CRF is unavailable when the investigator was informed of the ERIN, he/she should:

- **Immediately** fill in a paper "Adverse event" page:
 - For a serious event on a paper entitled "Adverse event – Initial information" page,

- For an event initially judged as non-serious on a paper entitled "Adverse event – Initial information" page, and the worsening leading to seriousness on a paper "Adverse event – Additional information" page,
- Immediately send the pages by fax or e-mail to the person(s) designated in the contact details provided in the investigator's study file. Should a Serious Adverse Event or any other reportable event need to be reported outside of the working hours, a phone call will be needed in addition to the expected written information transmitted by fax or by e-mail. The contact information to be used are the following:
 - o For European sites: dial the European international prefix followed by [name]
 - o For a Canadian site: dial the ICTR phone number listed in your investigator's study file.
 - o For a site in USA: contact the Ilkos medical monitor listed in your investigator's study file.
 - o In any case, the investigator can contact the central 24-hour phone line in France: [name]
- As soon as the e-CRF becomes available, the investigator should enter these data in the « Adverse Event » page of the e-CRF.

8.3.3. Responsibilities of the sponsor

In accordance with international guidances, the assessment of the seriousness and the causality of adverse events are usually made by the investigator but falls also under sponsor's duties, who is responsible for ensuring that all suspected unexpected serious adverse reactions are reported to Competent Authorities and Ethics Committees.

The sponsor will review the seriousness of the adverse events and the causality of the serious adverse events, whether reported by the investigator or upgraded by the sponsor. The causality and the seriousness may be upgraded (but never downgraded). Anonymized copies of documents providing useful information such as reports of further consultations, laboratory tests reports, reports of other examination aiding diagnosis may be asked for the event assessment. If the assessments of the investigator and the sponsor are different, both will be reported in the clinical study report.

Independently of the regulatory obligations of the investigator, the sponsor must report the pharmacovigilance data to the appropriate Authorities and to all the investigators involved, according to the requirements stated in ICH Good Clinical Practice guidelines and local regulations.

9. OTHER ASSESSMENTS NOT SPECIFICALLY RELATED TO EFFICACY OR SAFETY

9.1. Measurement of drug concentration

The concentrations of S42909 and its metabolites (S45015, S45236 and S55113) in plasma will be analysed according to validated methods by a central CRO (Algorithme Pharma). Procedures will be described in separate bio-analytical protocols established by (Algorithme Pharma).

9.1.1. Collection of blood samples

- Blood samples (6 ml) will be collected into lithium-heparinised tubes according to the tubes provided, each sample being intended for the assay of the parent drug and metabolites.
 - **In participants participating in the mandatory PK analysis only**, a total of 4 venous blood samples will be collected on the day of W000, W004, W006 study visits and one predose venous blood sample will be collected on the day of W001 and W002 study visits (see [Table \(4.2.2\) 2](#) - Pharmacokinetic Investigation schedule):
 - At W000, W004, W006 visits: prior to breakfast and first study drug intake at the end of the breakfast, which will be considered as T0, then 1h, 3h after drug intake and just before the participant leaves the site at the end of the study visit.
 - At W001, W002 visits: prior to breakfast and first study drug intake at the end of the breakfast.
 - **In participants participating in the mandatory and optional PK analyses** (see [Table \(4.2.2\) 2](#) - Pharmacokinetic Investigation schedule):
 - a total of 9 venous blood samples will be collected on the day of W000 visit, instead of the 4 blood samples listed above: prior to the breakfast and the first IMP intake at the end of the breakfast (T0) and 1h, 2h, 3h, 4h, 5h, 6h, 8h, 12h after first IMP intake. The 12h timepoint, which will be just prior to the dinner and the IMP intake at the end of the meal, can be adjusted to a maximum of 2 hours earlier to accommodate a more convenient dinner time.
 - at W001, W002 visits: prior to breakfast and first study drug intake at the end of the breakfast, which will be considered as T0.
 - a total of 13 venous blood samples will be collected on the day of W004 visit, instead of 4 blood samples listed above: prior to the breakfast and the first IMP intake at the end of the breakfast (T0) and 1h, 2h, 3h, 4h, 5h, 6h, 8h, 12h, after first IMP intake. The 12h timepoint, which will be just prior to the dinner and the IMP intake at the end of the meal, can be adjusted to a maximum of 2 hours earlier to accommodate a more convenient dinner time. PK sampling schedule for 13h, 14h, 15h and 24h is relative to the evening IMP administration (respectively 1, 2, 3 and 12h after evening IMP administration).
 - at W006 visit: prior to breakfast and first study drug intake at the end of the breakfast, which will be considered as T0, then 1h, 3h after drug intake and just before the participant leaves the site at the end of the study visit.
 - participants having signed the consent form for the optional PK analysis will stay during 12 hours at W000 and be hospitalized one day and one night at W004 visits.

Note: Participation in the CL2-42909-016 study does not imply a mandatory or systematic participation in the optional investigations. All voluntary participants will have to sign a specific informed consent form. The consent given for this analysis can be withdrawn at any moment without compromising the participation in the overall clinical study investigations. In addition, in case of consent withdrawal, related samples will be destroyed on a case by cases basis.

On the day of PK samples, well-balanced meals will be taken by the participants, equivalent to 600 Kcal for breakfast and 900-1100 Kcal for lunch and dinner with no more than 25% of

fat. The participants must consume all contents of their meals on these days. Examples of standard breakfast and lunch/dinner are provided in [Appendix 11](#).

- Plasma samples handling:

Blood samples will be centrifuged according to the laboratory manual instructions.

- After centrifugation, 4 aliquots of at least 0.5ml of clean plasma will be transferred into 4 cryovials tubes intended to assay the parent drug (S42909) and its metabolites (S45015, S45236 and S55113). Real time of sampling must be noted on the relevant page of the e-CRF.

Tubes will be clearly labelled with indelible ink, with labels provided with the tubes and stating for example:

- Protocol number (CL2-42909-016), Participant number, Treatment number, site number
- Visit, date of the sampling, time (e.g. W000, T12h).

